## Product Storage and Stability

Based on routine pharmacy practice and State Board of Pharmacy regulation, the storage condition is not specified on the labeling if the drug is to be stored at room temperature, which is the case for 18F-DCFPyL. Beyond-use date is 10 hours from EOS.

# Preparation

The study drug will be prepared and shipped by the radiopharmacy. They will label the injections with detailed information of the drug product for the clinical sites. It is in compliance with 21 CFR 312.6 requirements.

## 3.4.3.3 Measures to Minimize Bias: Randomization and Blinding

The study will not have randomized or blinding components. All participants will be provided with the intervention drug if they meet the inclusion criteria listed in section 3.2.1.

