# **STUDY SUMMARY**

Title	High-Resolution, 18F-PSMA PET-MRI for Mapping Prostate Cancer in Patients Considering Focal High-Intensity Focused Ultrasound (HIFU) Therapy or Radical Prostatectomy
Short Title	High resolution PET-MRI before prostate cancer HIFU or radical prostatectomy
Protocol Number	Pro00000832
Phase	Two parts: Phase II and Pilot
Methodology	Single arm, paired imaging (Phase II)
Study Duration	3 years
Study Center(s)	Cedars Sinai Medical Center
Objectives	Phase II Study (HIFU): Primary Endpoint: Number of additional biopsy-proven cancers that novel imaging modalities of hrMRI and/or F18-PSMA PET would detect when compared to reference standard imaging of mpMRI in patients undergoing HIFU procedure. Secondary Endpoint: Negative biopsy rate of standard 12-core biopsy 6 months following HIFU therapy.  Phase II Study (Radical Prostatectomy(RP)): Primary Endpoint: To determine the sensitivity in detection of prostatic carcinoma of novel imaging modalities of hrMRI and /or F18-PSMA PET compared to reference standard mpMRI in patients scheduled to undergo radical prostatectomy. Secondary Endpoint: Specificity of hrMRI, F18PSMA PET and mpMRI for detecting all tumors and metastasis at 6 months follow up.
Number of Subjects	30 Study Subjects (Phase II HIFU), 31 Study Subjects (Phase II RP)

Diagnosis and Main Inclusion Criteria	
 
Diagnosis for Pilot trial: Any patient scheduled to undergo radical prostatectomy Diagnosis: Clinically localized, unilateral, high-grade prostate cancer OR at high risk for having unrecognized high grade Prostate Cancer Inclusion Criteria:         
 
Biopsy consisting of ≥ 10 tissue cores sampled
 
PSA ≤20 ng/mL
 
cT1-cT2c
 
Either overall Gleason score ≥ 7 with Gleason grade 4 or 5 component localized to one lobe (i.e. right or left) OR overall Gleason score 6 with ≥ half of systematic biopsy cores positive and ≥ 50% of core involvement in at least one core
 
Patients considering focal HIFU therapy
 
Patients considering radical prostatectomy
 
 
 
		
Study Imaging	F18-PSMA PET-MRI in combination with multiparametric prostate MRI using high resolution DWI		
Control Imaging	Standard multiparametric prostate MRI		
Reference standard	MRI-targeted prostate biopsies will serve as the reference standard and all lesions seen on any MRI protocol will be biopsied. In the pilot trial, the prostatectomy pathology will serve as the reference standard.		

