## Pre-HIFU Imaging Protocol for Tumor Mapping

Eligible participants will then undergo mapping MRI in advance of HIFU therapy using both standard mpMRI and PET-hrMRI. All imaging will be completed in one sitting. hrMRI increases the length of the MRI by approximately 5 minutes. PET-MRI sequences increased the length of mpMRI by 30 minutes. Scanning will be done on the Siemens Biograph mMR scanner at the Research Imaging Core facility in the Davis Building.

Subjects undergoing a PET-hrMRI will be screened using the standard clinical protocol to determine whether it is safe to administer contrast to the subject.

PET scans involve injection of a radioisotope. Subjects undergoing a contrast-enhanced MR-PET will be screened using the standard clinical protocol to determine whether it is safe to administer contrast to the subject. An IV line will be inserted, and the participant will receive 9 mCi ±20% F18-PSMA injection diluted up to 10mL injected via the IV, as an IV bolus injection followed by 10mL flush with normal saline solution. The participant will then be positioned supine in the scanner and will be scanned in the area of the prostate. The time from end of injection of F18-PSMA injection to the start of imaging should be 60 minutes. For the PET acquisition, participants will be imaged for approximately 30 minutes.

All MRI images will be read according to PI-RADS (version 2) by a dedicated GU radiologist who has experience reading over 500 prostate MRIs. All PET scans will be read by nuclear medicine investigators on the study ([name]). All lesions with PI-RADS greater than or equal to 3 and all PET positive areas will be considered suspicious for cancer. A region of interest (ROI) application will be used. The circumference of a

suspicious lesion will be drawn on each individual MRI slice. The lesion volume and average ADC will be calculated from the ROI's. The tumor volumes and ADCs will be provided by the radiologist. To prevent the hrMRI from influencing the review of the mpMRI, all mpMRI's will be reviewed first. The radiologist will always be blinded to previous pathology.

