# **Incidental Findings**

Only noted clinically significant incidental findings will be communicated to the subject, per CSMC IRB and Legal Department approved policy, as a result of agreeing to undergo a research MRI scan. No reports or images will be provided to subjects and their medical records. However, MRI mapping results will be provided to the treating physicians who will use this information for MR/ultrasound guided prostate biopsy.

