# 6.2 Radical Prostatectomy Phase II Study

Our previously conducted pilot study investigating the impact of fluciclovine PET imaging on improving sensitivity of prostate cancer detection (identical to this study but using fluciclovine tracer instead of PSMA) was criticized due to lack of a gold standard based on radical prostatectomy (outcome was based on biopsy only). Since the HIFU arm in this PSMA PET study has a biopsy-only gold standard, we elected to include a parallel study arm using PSMA-PET imaging for intraprostatic cancer detection but using radical prostatectomy pathology as the gold standard. While there are historical references for sensitivity of PSMA-PET for intraprostatic cancer detection, they are not ideal to be used as a reference for our study since: they are few in number and may not provide generalizable estimates; the analysis to date has only been done on a per-patient (rather than a per-lesion) basis; and there is variation in reading of mpMRI by center/radiologist. The described parallel radical prostatectomy pilot arm will allow us to compensate for these limitations and describe this data in parallel with our HIFU analysis.

Power Assessment: The main hypothesis to be tested is whether the sensitivity of PSMA PET-hrMRI is 20% greater than mpMRI alone on a per lesion basis. It is expected 6 lesions in average per patient. Therefore, the power considerations are the same as presented for the HIFU cohort as displayed on Table 1.

**Table 1.** Power for McNemar test proposed by Yang et al. (2010) to detect a difference of 20% between sensitivities of the combination (PET-hrMRI or mpMRI) and mpMRI

Total Sample Size	# Patients with at least one positive biopsy section	Power
20	16	70.2
25	21	81.5
30	25	88.9
35	29	93.1
40	33	95.5

Statistical Analysis: Sensitivities will be compared using McNemar's type test proposed by Yang et al. (17,2010). for cluster matched binary data. In addition, the 95% confidence interval for difference between sensitivities will be calculated as proposed by Yang et al. (18,2012).

Secondary Endpoints: Specificity of imaging for detecting all tumors on prostatectomy

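### Nothing in the protocol keeps the pathology read, or the matching of scan marks to tumours, from being done with the scan results and modality in view; this matters most for the per-lesion prostatectomy endpoint

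*Combined protocol and SAP*

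**What the plan says.** Section 3.4.3.3, the protocol's only section on bias control, states "The study will not have randomized or blinding components". The sentence after it concerns who receives the tracer: "All participants will be provided with the intervention drug if they meet the inclusion criteria listed in section 3.2.1".

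The Pre-HIFU Imaging Protocol section does contain masking. "The radiologist will always be blinded to previous pathology", and the reading order is fixed: "To prevent the hrMRI from influencing the review of the mpMRI, all mpMRI's will be reviewed first". For PET it says only "All PET scans will be read by nuclear medicine investigators on the study".

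Reference standards:
- **HIFU arm:** the Study Summary says "MRI-targeted prostate biopsies will serve as the reference standard and all lesions seen on any MRI protocol will be biopsied". Section 6.1 analyses six sections of the prostate per patient.
- **Prostatectomy arm:** the reference is the prostatectomy pathology, and section 6.2 analyses per lesion, adding "It is expected 6 lesions in average per patient". Section 3.4.1 allows surgery at an outside hospital. The final report is then obtained and reviewed centrally, and slide review is left undecided.

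On release of results, Incidental Findings (section 4.0) keeps research reports and images out of the medical record but adds "MRI mapping results will be provided to the treating physicians who will use this information for MR/ultrasound guided prostate biopsy".

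**The concern.** Per-lesion sensitivity depends on a repeated judgement that a given scan mark and a given tumour focus are the same lesion. If the person judging sees which modality made the mark, doubtful matches can be settled in favour of the new test. If the pathologist knows where PET-hrMRI was positive, those areas may be searched more closely. Either would raise the measured sensitivity of PET-hrMRI over mpMRI without any better detection. The prostatectomy arm was added because an earlier study was criticised for having only a biopsy reference (section 6.2), so a reference open to the same kind of criticism would weaken the reason for the arm.

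**Working it through.** **1. Masking, step by step**

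| Step | What the plan provides | Where |
|---|---|---|
| MRI read | Radiologist blinded to previous pathology; mpMRI before hrMRI | Pre-HIFU Imaging Protocol |
| PET read | Readers identified; masking not mentioned | Same |
| Biopsy targets (HIFU) | Chosen from hrMRI and PET by design, plus a sextant template | Mapping Biopsy Protocols |
| Pathology read | No masking stated; research scans kept out of the medical record | Incidental Findings |
| Matching marks to tumours | No masking and no rule | 6.1, 6.2 |

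The first row contradicts the literal wording of 3.4.3.3. The last two rows are the gap. Keeping scans out of the record makes it less likely that a prostatectomy pathologist sees them. It cannot mask matching, which by its nature brings marks and pathology together.

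**2. Direction of error.** Table 1 compares the combination (PET-hrMRI or mpMRI) with mpMRI. Take a focus that neither scan truly showed. Wrongly credited to mpMRI, it enters both sensitivities and the difference is unchanged. Wrongly credited to PET-hrMRI only, it is all gain. A generous mpMRI credit lowers the difference only for a focus that PET-hrMRI already has. The errors therefore do not simply cancel.

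**3. Standard error implied by Table 1.** Inputs: a 20-point difference and 88.9% power at n=30 (Table 1). A two-sided 5% test is assumed, because the Study Summary gives alpha as 0.05 without stating sidedness.
- Check of the stated power: simulating the clustered test with the plan's inputs (mpMRI sensitivity 42%, the four correlations, 25 positive patients) gave 86.3% with a mean of 2.5 lesions per positive patient, and 91.8% with 2.5/0.82 = 3.05. These bracket 88.9%. The documents give too little simulation detail to reproduce it exactly, so the stated figure is used.
- SE = 20 / (1.960 + 1.221) = 6.29 points.

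**4. False-positive chance in favour of PET-hrMRI, with no true gain.** P = P(Z > 1.96 − bias/6.29).

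| Assumed spurious gain | 1.96 − bias/6.29 | Chance |
|---|---|---|
| 0 points | 1.960 | 2.5% |
| 2 points | 1.642 | 5.0% |
| 5 points | 1.165 | 12.2% |
| 10 points | 0.370 | 35.6% |

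**5. In lesions.** Table 1 was simulated with 2.5 lesions per patient, which is 25 × 2.5 = 62.5 to 30 × 2.5 = 75 lesions. A 5-point gain is then 0.05 × 62.5 = 3.1 to 0.05 × 75 = 3.75 wrongly credited lesions. If the prostatectomy arm really has 6 lesions per patient, it has 31 × 6 = 186 lesions at 100/186 = 0.54 points each, and 5 points is 0.05 × 186 = 9.3 lesions. The SE of 6.29 does not belong to that denominator, so the chances in step 4 should not be attached to it.

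**6. Cross-check by simulation.** Both true sensitivities were set at 42%, compared directly, in 25 positive patients, and a share f of PET-hrMRI misses was wrongly credited as hits. Two-sided rejection was 4.2% at f=0, 6.1% at f=5% (gain 3.0 points), 13.0% at f=10% (5.7 points) and 37.2% at f=20% (11.8 points). The step 4 formula gives 14.6% at 5.7 points and 47% at 11.8 points. The two agree in direction; the simulation is milder at the larger gain.

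**The case against.** The sentence in 3.4.3.3 sits under Study Intervention and leads into who receives the tracer. A reader might infer that the protocol rules out blinding altogether. The imaging protocol shows that it does not, so the supportable point is a conflict to reconcile and an omission to fill. This objection stands.

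A reader might also infer that the reference standard is therefore not independent of the index test. That does not follow. The documents are silent on whether assessors will know the scan results. Silence leaves a risk open but does not demonstrate dependence, and keeping research scans out of the medical record reduces the risk for the prostatectomy pathologist.

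The two arms are also not equally affected. In the HIFU arm the larger dependence is that scans direct where tissue is taken. That is intended, and masking would not remove it. Assigning marks to six sections also involves fewer fine judgements than matching lesions.

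Finally, the figure of 6 lesions in section 6.2 may be the six sections of 6.1 carried over, since 6.2 uses it to justify the same power table. And one might suppose that a broad PET-positive area would be credited with several foci. The documents give no mark sizes or coverage from which to size that effect.

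What survives is that no section masks the matching step or sets a rule for it, and keeping scans out of the record does not fill that gap.

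**Conclusion.** The point holds as an unprotected step, not as proven bias. Section 3.4.3.3 and the Pre-HIFU Imaging Protocol conflict on their face, and nothing in the protocol keeps pathology reading or scan-to-tumour matching from being done with results and modality in view. It matters most for the prostatectomy primary endpoint and much less for the HIFU arm. The clustered McNemar-type test allows for correlation within patients but has no means of correcting miscredited lesions.

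The percentages illustrate sensitivity to bias. They rest on an assumed spurious gain of 2 to 10 points, a two-sided 5% test, and a standard error taken from a simulation with 2.5 lesions per patient. The documents supply no miscrediting rate. This is a cheap improvement, not a defect that invalidates the design.

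**What to change.** Reconcile 3.4.3.3 with the Pre-HIFU Imaging Protocol, and replace the no-blinding sentence with wording such as:

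> No randomization. Image readers are masked as described under the imaging protocol. Prostatectomy tumour findings are recorded and locked without access to PET, hrMRI or mpMRI results. Scan marks are then matched to the locked record from coded marks with the modality hidden, under one prespecified matching rule applied identically to all modalities.

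Refer to this in 6.2, and in 6.1 for assigning marks to the six sections. For outside-hospital cases, apply the masked matching to whatever report or slides are obtained. Which matching rule to adopt is for the study team to decide. It should be fixed in advance, and a rule written for lesions need not suit the six-section analysis.

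Cost: protocol wording and a coding step by existing study staff, with no added patients or procedures. Downsides: scans can no longer guide how the specimen is examined, and the measured gain may be slightly smaller.

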## **3.4.3.4** Study Intervention Compliance

Physicians will recruit patients that meet the inclusion criteria for the study. Throughout the process, patients will be monitored by the physician and the study team assisting with the trial. They will keep track of the administration of 18F-PSMA by entering it on RedCap, a software used to capture data for research studies. The study staff will follow up with the patient if needed.

## **3.4.3.5** Concomitant Therapy and Rescue Medicine

Not applicable to this study

## Pre-HIFU Imaging Protocol for Tumor Mapping

Eligible participants will then undergo mapping MRI in advance of HIFU therapy using both standard mpMRI and PET-hrMRI. All imaging will be completed in one sitting. hrMRI increases the length of the MRI by approximately 5 minutes. PET-MRI sequences increased the length of mpMRI by 30 minutes. Scanning will be done on the Siemens Biograph mMR scanner at the Research Imaging Core facility in the Davis Building.

Subjects undergoing a PET-hrMRI will be screened using the standard clinical protocol to determine whether it is safe to administer contrast to the subject.

PET scans involve injection of a radioisotope. Subjects undergoing a contrast-enhanced MR-PET will be screened using the standard clinical protocol to determine whether it is safe to administer contrast to the subject. An IV line will be inserted, and the participant will receive 9 mCi ±20% F18-PSMA injection diluted up to 10mL injected via the IV, as an IV bolus injection followed by 10mL flush with normal saline solution. The participant will then be positioned supine in the scanner and will be scanned in the area of the prostate. The time from end of injection of F18-PSMA injection to the start of imaging should be 60 minutes. For the PET acquisition, participants will be imaged for approximately 30 minutes.

All MRI images will be read according to PI-RADS (version 2) by a dedicated GU radiologist who has experience reading over 500 prostate MRIs. All PET scans will be read by nuclear medicine investigators on the study ([name]). All lesions with PI-RADS greater than or equal to 3 and all PET positive areas will be considered suspicious for cancer. A region of interest (ROI) application will be used. The circumference of a

suspicious lesion will be drawn on each individual MRI slice. The lesion volume and average ADC will be calculated from the ROI's. The tumor volumes and ADCs will be provided by the radiologist. To prevent the hrMRI from influencing the review of the mpMRI, all mpMRI's will be reviewed first. The radiologist will always be blinded to previous pathology.

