Statistical analysis	Our hypothesis is that 20% of biopsy-proven tumors will be detected on PET-hrMRI and not on standard MRI. If we assume that no biopsy proven tumors will only be detected on standard MRI, at alpha=0.05, n=40 provides a power of at least 90% when we account for 5 cases that will not be evaluable. The RP phase II study is a parallel study arm using PSMA-PET imaging for intraprostatic cancer detection, but using radical prostatectomy pathology as the gold standard. The radical prostatectomy pilot arm will allow us to compensate for limitations and describe this data in parallel with the HIFU analysis.		

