## 2.6 PSMA and PET-MRI in Prostate Cancer

Positron emission tomography (PET) imaging has been increasingly used for detection of occult distant metastases in patients with advanced prostate cancer using prostate-cancer-specific radiotracers (PSMA) or radiotracers that accumulate preferentially within prostate cancer tissue (11C choline, 11C acetate, and 18F fluciclovine). Prostate-specific membrane antigen (PSMA) is a type II membrane protein originally characterized by the murine monoclonal antibody (mAb) 7E11-C5. 3 and is expressed in all forms of prostate tissue, including carcinoma. F18-PSMA is a radiolabeled antibody that binds to PSMA antigen expressed on the surface of the prostatic cancer cells.

While PET technology is usually paired with CT imaging for 3D localization due to wide availability of CT technology, there have been efforts to pair PET technology with MRI to improve identification of lesions both within and outside of the prostate gland, given the advantages in spatial resolution of MRI over CT imaging. While mpMRI is a very sensitive imaging modality for identifying localized prostate cancers, its specificity is limited; colocalization of tumors identified on MRI with PET imaging may be able to improve specificity to account for this limitation.

Early work has suggested that co-localization of this PET radiotracer with 3-D mpMRI imaging may enhance accuracy of localization of intraprostatic cancer lesions compared with mpMRI or PET/CT alone. In a study of 21 patients who underwent 18F-fluciclovine PET/CT and mpMRI prior to radical prostatectomy, combined 18F-fluciclovine PET/CT and mpMRI imaging yielded a positive predictive value of 82% for tumor localization, which

was significantly higher than that with either modality alone.

This would suggest that pairing also F18-PSMA PET imaging with MRI directly may improve localization of cancers within the prostate for HIFU treatment planning. We hypothesize that further leveraging the sensitivity and spatial resolution of hrMRI with the specificity of PET imaging may further enhance performance in accurately identifying cancers within the prostate.

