## 3.3 Study endpoints

Primary Endpoint (HIFU): Number of additional biopsy-proven cancers that novel imaging modalities of hrMRI and/or F18-PSMA PET would detect when compared to reference standard imaging of mpMRI in patients undergoing HIFU procedure.

Secondary Endpoint (HIFU): Negative biopsy rate on standard 12-core biopsy 6 months following HIFU therapy.

**Primary Endpoint (Prostatectomy):** To determine the sensitivity in detection of prostatic carcinoma of novel imaging modalities of hrMRI and/or F18-PSMA PET compared to reference standard mpMRI in patients scheduled to undergo radical prostatectomy.

Secondary Endpoint (Prostatectomy): Specificity of hrMRI, F18-PSMA PET and mpMRI for detecting all tumors and metastasis at 6 months follow up.

**Exploratory Endpoint:** RNAseq transcriptome analysis of lesions that are positive on mapping biopsy. Sensitivity and specificity of PET-hrMRI for detecting all tumors detected on prostatectomy pathology.

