#### 6.0 STATISTICAL ANALYSIS

# 6.1 HIFU Phase II Study

Our preliminary data suggests that up to 60% of tumors invisible to standard mpMRI are detected on hrMRI in an active surveillance population. It is unclear how many additional lesions will be identified on PSMA PET-MRI. Since all areas of concern will be biopsied and only biopsy-proven tumors will be treated with HIFU, the morbidity of the surgical intervention is minimized and its potential to achieve cure is maximized.

Power Assessment: The main hypothesis to be tested is whether the sensitivity of PSMA PET-hrMRI is greater than mpMRI alone in 20% considering the prostate divided in 6 sections for each patient. The power is evaluated using 1000 simulations based on the McNemar's type test proposed by Yang et al. (17,2010). Data is generated based on four correlations: r1: between lesions evaluated by PSMA PET-hrMRI for the same patient, r2: between lesions evaluated by mpMRI for the same patient, r3: between evaluations PSMA PET-hrMRI and mpMRI for the same lesion and r4: between evaluations PSMA PET-hrMRI and mpMRI for the different lesions at the same patient. Based on preliminary data, we estimated mpMRI sensitivity of 42%, (r1, r2, r3, r4) = (-0.249, -0.119, 0.714, -0.172) using Spearman correlation, average number of lesions of 2.5 per patient and prevalence of patients with at least one positive biopsy section equal to 82%. The results are presented in Table 1.

**Table 1.** Power for McNemar test proposed by Yang et al. (2010) to detect a difference of 20% between sensitivities of the combination (PET-hrMRI or mpMRI) and mpMRI

Total Sample # Patients with at least one positive biopsy
Size section Power

20	16	70.2
25	21	81.5
30	25	88.9
35	29	93.1
40	33	95.5

The minimum sample size to reach at least 85% of power is 30 patients with complete imaging data. Patients with incomplete imaging data will be replaced.

Statistical Analysis: Sensitivities will be compared using McNemar's type test proposed by Yang et al. (17,2010). for cluster matched binary data. In addition, the 95% confidence interval for difference between sensitivities will be calculated as proposed by Yang et al. (18,2012).

Secondary Endpoints: Negative biopsy rate within treatment zones on standard 12-core biopsy 6 months following HIFU therapy; rate of high grade cancer in the untreated lobe.

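### The HIFU arm judges imaging only by cancers gained or sensitivity, so a significant gain cannot separate a better scan from one that marks more of the gland

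*Combined protocol and SAP*

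**What the plan says.** **Reading rule** (Pre-HIFU Imaging Protocol for Tumor Mapping): "All lesions with PI-RADS greater than or equal to 3 and all PET positive areas will be considered suspicious for cancer". The Mapping Biopsy Protocols section takes a sextant template in every patient and targets lesions that are positive on hrMRI or on PET.

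**HIFU primary endpoint** (Section 3.3): "Number of additional biopsy-proven cancers that novel imaging modalities of hrMRI and/or F18-PSMA PET would detect", relative to mpMRI.

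**HIFU analysis** (Section 6.1): "The main hypothesis to be tested is whether the sensitivity of PSMA PET-hrMRI is greater than mpMRI alone in 20" per cent, tested with a McNemar-type method for clustered pairs. The Table 1 title describes a different comparison, namely power to "detect a difference of 20% between sensitivities of the combination (PET-hrMRI or mpMRI) and mpMRI". The secondary endpoints are the 6-month negative biopsy rate and high-grade cancer in the untreated lobe.

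**Specificity.** Section 2.6 says that "colocalization of tumors identified on MRI with PET imaging may be able to improve specificity". Section 3.3 lists specificity as a secondary endpoint of the prostatectomy arm (hrMRI, PET and mpMRI) and, as exploratory, sensitivity and specificity of PET-hrMRI against prostatectomy pathology. No section lists it for the HIFU arm. No section in either arm defines an analysis of sites positive on both hrMRI and PET.

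**The concern.** Under an either-positive rule, extra marks can raise sensitivity or leave it unchanged, but never lower it. This is so whether or not the marks carry information. Their cost falls on cancer-free sections, which the HIFU-arm analysis does not examine. A significant result there could mean that PET-hrMRI maps cancer better, or only that it marks more tissue.

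The case made for PET rests largely on specificity. Section 1.0 speaks of highly specific targeting. The supporting study in Section 2.6 is reported as a positive predictive value of 82% for combined PET and mpMRI. The HIFU arm, where the map guides focal treatment, reports neither quantity.

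**Working it through.** **1. The plan's own power figure.** Inputs from Section 6.1: mpMRI sensitivity 0.42; target 0.42 + 0.20 = 0.62; correlations −0.249, −0.119, 0.714, −0.172; 2.5 lesions per patient; 25 of 30 patients with a positive section. Alpha is 0.05 (Study Summary). Assumed here: a two-sided test, 2 or 3 lesions per positive patient, and the correlations acting on a latent-normal scale. Simulated power at 25 positive patients (2,000 runs):

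| Test | Power |
|---|---|
| Clustered, centred variance | 89.2% |
| Plain McNemar | 88.6% |
| Clustered, null variance | 86.6% |
| Table 1 | 88.9% |

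The stated figure is reproduced. In this model 24.7% of lesions are found only by the new read and 4.7% only by mpMRI (24.7 − 4.7 = 20.0). A true union with mpMRI allows no mpMRI-only lesions. With a 20% gain and no losses, power would be about 96% to over 99%, depending on the test. The Table 1 figures therefore fit a comparison that allows losses, while its title describes one that does not.

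**2. Random marking and the expected gain.** Let an add-on mark each section with probability *f*, unrelated to cancer.
- Union sensitivity = 0.42 + 0.58*f*, so the gain is 0.58*f*.
- 0.58*f* = 0.20 gives *f* = 0.345, or 6 × 0.345 = 2.07 sections per patient.
- The same holds for PET-hrMRI against mpMRI if hrMRI makes the same calls as mpMRI and PET marks at random.

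**3. One random section of six.** Take 25 positive patients with 2 or 3 positive sections each (62.5 on average).
- Chance of a gained section per patient: (2.5/6) × 0.58 = 0.242.
- Expected number gained: 25 × 0.242 = 6.04. Gain: 6.04/62.5 = 9.7 points.
- With at most one gain per patient and no losses, the clustered statistic Σd/√Σd² equals √b for b gains. It exceeds 1.96 when b ≥ 4. Binomial(25, 0.242) gives P(b ≥ 4) = 0.887.
- Exact two-sided McNemar: p = 2 × 0.5^b, which is 0.063 at b = 5 and 0.031 at b = 6. P(b ≥ 6) = 0.58.
- An observed 20 points needs about 13 gains; P(b ≥ 13) = 0.002.

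**4. Two random sections.** Expected gain: 2 × 0.58/6 = 19.3 points. Simulated significance is 99.8% on the clustered statistic and about 99% by exact McNemar.

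**5. The less favourable case.** If the whole PET-hrMRI read were random and compared alone with mpMRI, it would have to mark 62% of sections (3.7 of 6) for a 20-point gain. It would then be significant in about 57% of runs.

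**6. What a false-positive measure would show.** The documents give no mpMRI specificity; assume 0.80 (range 0.70 to 0.90). At *f* = 0.345:
- Union specificity = 0.80 × 0.655 = 0.52 (0.46 to 0.59), a loss of 28 points (24 to 31).
- Cancer-free sections in 30 patients: 180 − 62.5 = 117.5. Extra false positives: 117.5 × 0.276 = 32 (28 to 36).
- Cancer sections gained: 62.5 × 0.20 = 12.5.

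The sensitivity analysis sees the 12.5 and not the 32.

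**The case against.** Several stronger readings are tempting, and the documents do not support them.

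- **That the reading rule contradicts the study hypothesis.** The specificity statement in Section 2.6 is conditional background; the hypothesis tested is sensitivity. The quoted rule decides what is suspicious and is then used to choose biopsy targets. Sampling every either-positive area is sound, and it is what makes a predictive-value or both-positive analysis possible.
- **That an uninformative scan easily meets a 20-point success criterion.** Twenty points is a planning difference; the test is against zero. One random section is often significant but almost never reaches 20 points.
- **That only gains count.** This fits the endpoint wording, the Table 1 title and the Study Summary's assumption of no mpMRI-only tumors. It does not fit the hypothesis sentence in 6.1, under which a McNemar-type test also counts mpMRI-only cancers.
- **That hrMRI-or-PET must be less specific than mpMRI.** An either-positive rule cannot be more specific than its own components. mpMRI is a component only under the Table 1 title. Section 2.5 reports an AUC of 0.88 with high-resolution DWI against 0.72 for mpMRI.
- **That specificity is neglected.** The prostatectomy arm plans it, and that arm was added because biopsy is an imperfect reference. An uninformative PET could be exposed there.

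Two further points stand. The equal-calls assumption for hrMRI is unfavourable to the scan, given the preliminary sensitivities of 95.7% and 60.9%. Section 6.1 also notes that only biopsy-proven tumors are treated, so a false positive costs biopsy cores and not ablation.

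None of this supplies a false-positive measure in the HIFU arm or a both-positive read in either arm.

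**Conclusion.** The concern holds as a gap in what the HIFU arm analyses; the rule for selecting areas to biopsy is not at fault. A significant sensitivity gain there would not by itself show that the new map is better, because extra marking alone can produce it. Under the union comparison, or if hrMRI repeats the mpMRI calls, random marking of about 34% of sections gives an expected 20 points. Two random sections per patient are then almost certain to be significant; one is significant in roughly 58% to 89% of trials, depending on the test. If a wholly random read is compared alone, the risk is lower and needs far heavier marking.

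These figures rest on a two-sided 0.05 test, 2 or 3 positive sections per positive patient, and marks unrelated to cancer. The false-positive counts also rest on an assumed mpMRI specificity. This is an inexpensive improvement that changes what a positive HIFU-arm result can support; it does not invalidate the sensitivity test.

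**What to change.** No change to the either-positive rule for choosing biopsy targets is needed. In Sections 3.3 and 6.1, pre-specify as HIFU-arm secondary measures:

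1. Positive predictive value of targeted sites and benign targets per patient, for hrMRI, PET, hrMRI-or-PET and, where mpMRI lesions were sampled, mpMRI.
2. The paired change in false-positive sections against the mapping biopsy. State that biopsy can miss tumors and that marked sections receive extra cores.
3. The call positive on both hrMRI and PET, as a secondary read. Add this in the prostatectomy arm (Section 6.2) as well.

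Report the sensitivity gain together with measure 2.

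Two inconsistencies must be reconciled for these to be defined:
- whether the comparison is PET-hrMRI against mpMRI (hypothesis sentence in 6.1) or the union against mpMRI (Table 1 title);
- whether lesions seen only on mpMRI are targeted. The Study Summary and Section 1.0 include them; Section 3.1, the HIFU calendar footnote in 3.4.2 and the Mapping Biopsy Protocols name only hrMRI or PET lesions.

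The cost is protocol wording and some tabulation from reads and biopsies already planned, with no new scans or procedures. The downside is a little more analysis, and a headline gain shown beside its false-positive cost.
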